- Any other condition which, in the opinion of the investigator, would impede compliance or hinder completion of the study, including inability to swallow treatment capsules
- Failure or inability to give informed consent

Sample size / Power:

- Total sample size = 200; 50 per group
- Power = 90%
- Type I error (2-sided) = 5%
- Increase in sample size due to missing data = 10%
- Mean (SD) difference (Vitamin E – Placebo) in relative change [(BL-FU)/BL] in ALT at 24 weeks = 20% (31%)
 - Mean relative change (%) in ALT at 24 weeks in placebo = 20% (based on data from PIVENS trial)
 - Mean relative change (%) in ALT at 24 weeks in Vitamin E = 40% (based on data from PIVENS trial)
- Method of analysis = Williams' test for minimum effective dose

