9 STATISTICAL CONSIDERATIONS

9.1 STATISTICAL HYPOTHESES

- Primary Efficacy Endpoint(s): That one of the doses of vitamin E at 133.4 mg (200 IU), 266.8 mg (400 IU), or 533.6 mg (800 IU) daily is the minimum effective dose for improving relative change in alanine aminotransferase (ALT) from baseline to 24 weeks.
- Secondary Efficacy Endpoints(s): That one or more of vitamin E at 133.4 mg (200 IU), 266.8 mg (400 IU), or 533.6 mg (800 IU) daily is better than placebo in improving:
 - Proportion of patients achieving normalization* of ALT at 24 weeks
 - Mean change in ALT from baseline to 24 weeks
 - Mean change in AST and GGT from baseline to 24 weeks
 - Mean change in hepatic fat determined by FibroScan® CAP score from baseline to 24 weeks
 - Mean change in liver stiffness as assessed by FibroScan® from baseline to 24 weeks
 - Time course and end of treatment improvement in ALT, AST, GGT, and alkaline phosphatase
 - Time course and end of treatment improvement in C-reactive protein (serum marker of inflammation)
 - Time course and end of treatment improvement in change in total cholesterol, LDL cholesterol, HDL cholesterol, and serum triglycerides
 - Changes in fasting glucose levels from baseline to 24 weeks
 - Change in anthropometric measurements (weight, BMI, waist to hip ratio, waist circumference) from baseline to 24 weeks
 - Change in symptom assessment scores from baseline to 24 weeks
 - Change in frequency of CTCAE defined adverse events from baseline to 24 weeks
 - Mean change in ALT from 24 to 48 weeks (post-treatment).

- Mean change in AST and GGT from 24 to 48 weeks (post-treatment).
- Mean change in hepatic fat determined by FibroScan® CAP score from 24 to 48 weeks (post-treatment).
- Mean change in liver stiffness as assessed by FibroScan® from 24 to 48 weeks (post-treatment).

*Normalization of ALT is defined as a decrease in ALT to less than or equal to the ULN at the 24 week visit among participants who had an ALT value greater than ULN at baseline. Values for ULN are defined at each clinical center per institutional guidelines.

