9.4.3 ANALYSIS OF THE SECONDARY ENDPOINT(S)

For each secondary endpoint:

- Analyses of secondary endpoints are not dependent on findings of the primary endpoint or on the results of the Williams' test performed on the primary endpoint.
- Analyses will use complete case subjects of the Intention-to-Treat (ITT) Analysis Dataset (i.e., all randomized participants with complete data on each specific secondary endpoint).

The analysis of the 16 secondary endpoints listed in Section 3, Objectives and Endpoints, endpoints will use ANCOVA for continuous endpoints, logistic regression for binary endpoints, and Poisson regression for counts. Complete case analyses will be used for each secondary endpoint, if missing data on that endpoint < 10% and multiple imputation will be used if missing data on the secondary endpoint is 10% or greater. The covariate in the continuous endpoint ANCOVA models will be the baseline value of the continuous endpoint. Sensitivity analyses include use of non-parametric and influence-reducing regression for continuous endpoints (lowess plots and robust regression) and generalized linear models with scale factor estimation to account for under- or over-dispersion for binary endpoint data (dispersion-corrected logistic regression) and count endpoint data (dispersion-corrected negative binomial regression). Each secondary endpoint in the planned table of 16 secondary endpoints will be compared across the 3 vitamin E doses vs Placebo using treatment effect estimates, 95% confidence limits, and p-values. The Benjamini-Hochberg Method will be use to adjust the presented p-values for the false discovery rate (FDR) from the 16x3=48 pairwise p-values.

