9.4.4 SAFETY ANALYSES

Safety data will be presented by treatment group to the Data and Safety Monitoring Board during the course of the trial. Each adverse event will be displayed showing AE name per the CTCAE v5.0 when applicable, class, severity, patient ID, clinic, treatment group, time since randomization, resolution status and physician's assessment of relatedness to treatment. Patient-specific summary tables including any adverse event (yes vs no), frequency of multiple adverse events (i.e., 0, 1, 2, 3+) and highest severity of adverse event (none, mild, moderate, severe, life-threatening) will be displayed by treatment group along with p-values from Fisher's exact tests.

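### The adverse-event comparison sits inside the Benjamini-Hochberg family of efficacy tests, which weakens the plan's only explicit dose-versus-placebo test of adverse-event frequency

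*Combined protocol and SAP*

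**What the plan says.** Section 9.1 lists the secondary endpoints under a single efficacy hypothesis, that one or more doses beat placebo. Among them is "Change in frequency of CTCAE defined adverse events from baseline to 24 weeks". The justification column in section 3 acknowledges that the secondary list contains safety outcomes.

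Section 9.4.3 then treats all rows alike: "Each secondary endpoint in the planned table of 16 secondary endpoints will be compared across the 3 vitamin E doses vs Placebo", with effect estimates, 95% confidence limits and p-values. Counts are analysed by Poisson regression. On multiplicity it says: "The Benjamini-Hochberg Method will be use to adjust the presented p-values for the false discovery rate (FDR) from the 16x3=48 pairwise p-values". No row is exempted and no false discovery rate level is named. The only error rate stated is the trial's "Type I error (2-sided) = 5"%.

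Section 9.4.4 separately plans patient-level adverse-event tables (any event; 0, 1, 2 or 3+ events; highest severity). These "will be displayed by treatment group along with p-values from" Fisher's exact tests. It mentions no adjustment and does not specify dose-versus-placebo contrasts.

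**The concern.** Controlling the false discovery rate protects readers against too many spurious benefit claims. For a safety outcome the costlier error is usually the missed signal, and an upward adjustment for dozens of efficacy tests makes that error more likely. Here the adverse-event p-value at a given dose would depend on how many lipid, weight or enzyme comparisons happened to be significant, which tells the reader nothing about safety.

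This matters in a dose-finding trial whose risk-benefit case (section 2.3.3) is that a lower effective dose may avoid long-term adverse effects. A real excess at one dose could be printed with an adjusted p-value above 0.05. The plan would also carry two sets of adverse-event p-values, one adjusted and one apparently not, without saying which governs.

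**Working it through.** **Family size.** The section 9.1 list has 16 rows: ALT normalization; ALT change; AST/GGT change; CAP; stiffness; enzyme time course; CRP; lipids; glucose; anthropometry; symptoms; adverse events; and four post-treatment rows (ALT, AST/GGT, CAP, stiffness). 16 x 3 doses = 48, which reproduces the plan's figure. Adverse events supply 3 p-values and the other rows 48 − 3 = 45. Six rows (18 p-values) are liver enzymes, for example "Time course and end of treatment improvement in ALT, AST, GGT, and alkaline phosphatase". Ten rows (30 p-values) are not.

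**Inputs.**
- From the documents: 50 per group and 10% missing data, so 45 evaluable; design effect 20 points with SD 31 (section 9.2).
- Assumed: level q = 0.05; the design effect applies to the active enzyme rows; one p-value per row and dose; two-sided tests.

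**Cut-off for the adverse-event row.** If k other comparisons are rejected, the next p-value must be at or below t = 0.05 × (k + 1)/48. Take a top-dose excess with 80% power at unadjusted 5%, so its expected z is 1.96 + 0.84 = 2.80. Power at cut-off t is Φ(2.80 − z at 1 − t/2).

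| Other rejections k | Cut-off t | Power |
|---|---|---|
| Unadjusted | 0.05 | 80% |
| 0 | 0.05/48 = 0.0010 | 32% |
| 4 | 0.0052 | 50% |
| 8 | 0.0094 | 58% |
| 12 | 0.0135 | 63% |
| 18 (every enzyme comparison) | 0.0198 | 68% |

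**Simulation.** In practice k varies, because each active enzyme comparison has expected z of (20/31) × √(45/2) = 3.06 and does not always reject. Simulating the 48 tests with a shared placebo arm, with four or six enzyme rows active at one, two or three doses, gives:
- no enzyme effect: about 32%;
- enzyme rows responding: about 45 to 62%, and the ends move by a point or so with the assumed correlations;
- adverse events kept in a separate family of the 30 non-enzyme p-values: about 37%;
- adverse events outside any family: 80%.

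**Illustration with counts (assumed rates).** Take 1.0 versus 1.5 events per patient and 50 per arm. The standard error of the log rate ratio is √(1/50 + 1/75) = 0.183, and ln 1.5 = 0.405, so expected z is about 2.22. Power is 60% at 0.05, 46% at 0.0198 and 15% at 0.0010.

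**The non-enzyme efficacy rows.** If enzymes respond at the design effect and nothing else does, the chance of at least one false claim among the non-enzyme rows is 9 to 26% in the pooled family (7 to 32% over a wider range of assumed correlations). It is about 3% with no enzyme effect, 4 to 7% at half the design effect, and about 4% if those rows had their own family. In the same settings the false-claim rate per non-enzyme comparison is 0.4 to 1.7%, and the false discovery rate over all 48 stays at 3 to 5%.

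**The case against.** The best defence is that safety is handled elsewhere. Section 9.4.4 has its own Fisher's exact tests with no stated adjustment. Sections 8.3.5 and 10.1.6 provide for regular DSMB review, including comparisons of adverse-event rates by treatment group. Section 9.4.3 still reports an estimate and 95% confidence limits for the adverse-event row; only the p-value is adjusted. This stands, and it rules out saying that the signal is suppressed. It does not remove the point. The Fisher tests are by treatment group, with counts collapsed at 3+, and do not replace the pairwise comparison of event counts, which is the one adjusted.

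A reader might infer that the enzyme rows cause the adverse-event loss. The figures show the reverse: enzyme rejections relax the cut-off (45 to 62%, against 32% without them and 37% in a separate non-enzyme family).

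A reader might also infer that false claims on liver fat, stiffness, lipids or weight run at 10 to 30%. That is the chance of at least one false rejection among 30 null comparisons, conditional on a design-size enzyme effect; it is not a rate of false claims. The plan promises false discovery rate control over all 48, and that holds. It also treats outcomes such as CAP as certainly null, although section 2.2 cites earlier evidence of an effect on steatosis. Finally, one family is a legitimate pre-specified choice, as is the statement that "Analyses of secondary endpoints are not dependent on findings of the primary endpoint".

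**Conclusion.** The concern holds for the adverse-event row. Sections 9.1 and 9.4.3 together place a safety outcome in an efficacy false discovery rate family. The chance of flagging a top-dose excess that would have 80% power unadjusted falls to about 32% with no enzyme response and about 45 to 62% with one. This rests on q = 0.05, which the plan does not state, 45 evaluable per arm, and design-size effects on the responding enzyme rows. The consequence is a weakened pairwise test, partly offset by section 9.4.4 and DSMB review.

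The documents do not support requiring a split between enzyme and non-enzyme efficacy rows. Splitting lowers the chance of any false non-enzyme claim from 9 to 26% to about 4% when enzymes respond. But a real non-enzyme effect with 80% unadjusted power would then be detected in about 37% of trials instead of 45 to 62%. The trial team may reasonably decide either way.

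**What to change.** In section 9.4.3, remove the adverse-event row from the Benjamini-Hochberg adjustment, change the count to 15 x 3 = 45 p-values, and state the false discovery rate level. In section 9.4.4, add the dose-versus-placebo rate ratios for adverse-event frequency with 95% confidence intervals and unadjusted p-values, and say that these are not adjusted for multiplicity. Amend sections 3 and 9.1 so that the row is labelled a safety outcome.

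No change to data, visits or sample size is needed. The cost is more chance adverse-event flags: with three unadjusted tests at 5%, the probability of at least one, in either direction, is at most 3 × 5% = 15%. The remaining efficacy rows are hardly affected; the strictest cut-off moves from 0.05/48 = 0.00104 to 0.05/45 = 0.00111.

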3 OBJECTIVES AND ENDPOINTS

OBJECTIVES	ENDPOINTS	JUSTIFICATION FOR ENDPOINTS
Primary		
The primary objective is to determine the minimum effective dose of vitamin E (133.4 mg, 266.8 mg, or 533.6 mg) at which measures of NAFLD are improved	Relative change in ALT at week 24 from baseline [i.e., (ALT at baseline – ALT at week 24)/ ALT at baseline]	ALT is the most accepted short term (<12 months) surrogate marker for histologic improvement in NAFLD.
Secondary		
The secondary objectives have been selected to provide further information on the minimum effective dose of vitamin E needed to improve measures of NAFLD progression, and to provide information on the post-treatment effects of vitamin E on the liver.	Proportion of patients achieving normalization* of ALT at 24 weeks Mean change in ALT from baseline to 24 weeks Mean change in AST and GGT from baseline to 24 weeks Mean change in hepatic fat determined by FibroScan® CAP score from baseline to 24 weeks Mean change in liver stiffness as assessed by FibroScan® from baseline to 24 weeks Time course and end of treatment improvement in ALT, AST, GGT, and alkaline phosphatase Time course and end of treatment improvement in C-reactive protein (serum marker of inflammation)	These endpoints were selected because they measure important co-morbidities of NAFLD and are useful for determining if vitamin E improves other features commonly associated with NAFLD. Safety and quality of life outcomes are also included.

OBJECTIVES	ENDPOINTS	JUSTIFICATION FOR ENDPOINTS
	
Time course and end of treatment improvement in change in total cholesterol, LDL cholesterol, HDL cholesterol, and serum triglycerides
 
Changes in fasting glucose levels from baseline to 24 weeks
 
Change in anthropometric measurements (weight, BMI, waist to hip ratio, waist circumference) from baseline to 24 weeks
 
Change in symptom assessment scores from baseline to 24 weeks
 
Change in frequency of CTCAE defined adverse events from baseline to 24 weeks
 
Mean change in ALT from 24 to 48 weeks (post-treatment).
 
Mean change in AST and GGT from 24 to 48 weeks (post-treatment).
 
Mean change in hepatic fat determined by FibroScan® CAP score from 24 to 48 weeks (post-treatment).
 
Mean change in liver stiffness as assessed by FibroScan® from 24 to 48 weeks (post-treatment).
	
Tertiary/Exploratory		

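### Section 9.4.3 sets the false discovery rate family at 48 p-values by counting rows, but the listed endpoints give 72 to 81 comparisons and nothing says how these become 48

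*Combined protocol and SAP*

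**What the plan says.** Section 9.4.3 takes its endpoints from the objectives table: "The analysis of the 16 secondary endpoints listed in Section 3, Objectives and Endpoints". Each of these "will be compared across the 3 vitamin E doses vs Placebo using treatment effect estimates, 95% confidence limits, and p-values". Benjamini-Hochberg is then used "to adjust the presented p-values for the false discovery rate (FDR) from the 16x3=48 pairwise p-values".

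The list in Section 3, repeated in Section 9.1, does have 16 rows. Some rows carry one variable. Others carry several, for example "Mean change in AST and GGT from baseline to 24 weeks", "Time course and end of treatment improvement in ALT, AST, GGT, and alkaline phosphatase" and "Change in anthropometric measurements (weight, BMI, waist to hip ratio, waist circumference) from baseline to 24 weeks". The lipid row covers "total cholesterol, LDL cholesterol, HDL cholesterol, and serum triglycerides".

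For the models, 9.4.3 names ANCOVA for continuous endpoints, with the endpoint's own baseline as covariate, logistic regression for binary endpoints and Poisson regression for counts. It describes no composite, no multivariate test and no rule for picking one variable from a row that names several. It gives no FDR level.

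**The concern.** Benjamini-Hochberg compares the k-th smallest p-value with k/m times the chosen level, so the family size m is a working part of the procedure. The plan fixes m at 48 by treating each row as one endpoint. An ANCOVA with its own baseline covariate handles one outcome. It cannot return one p-value for four lipids or four body measurements together. The listed endpoints and the stated models therefore do not produce 48 p-values.

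What is at stake is the column of adjusted p-values in the main secondary table. Two analysts could follow the same sentence and print different values. Under some implementations the false discovery rate would exceed its level, or some comparisons would escape adjustment.

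**Working it through.** **Inputs.** The rows come from Section 3 (same list in 9.1). The three dose-versus-placebo comparisons and the family of 48 come from 9.4.3. The FDR level q is not in the documents; I assume 5% and show 10% as well.

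**Step 1. The plan's figure.** 16 rows x 3 doses = 48. This reproduces exactly.

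**Step 2. Variables per row.**

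| Row | Content | Variables |
|---|---|---|
| 1 | ALT normalization, week 24 | 1 |
| 2 | ALT, to week 24 | 1 |
| 3 | AST, GGT, to week 24 | 2 |
| 4 | CAP, to week 24 | 1 |
| 5 | Liver stiffness, to week 24 | 1 |
| 6 | ALT, AST, GGT, alkaline phosphatase (time course and end of treatment) | 4 |
| 7 | CRP (time course and end of treatment) | 1 |
| 8 | Four lipids (time course and end of treatment) | 4 |
| 9 | Fasting glucose | 1 |
| 10 | Four anthropometric measures | 4 |
| 11 | Symptom scores | 1 |
| 12 | Adverse event frequency | 1 |
| 13 | ALT, post-treatment | 1 |
| 14 | AST, GGT, post-treatment | 2 |
| 15 | CAP, post-treatment | 1 |
| 16 | Liver stiffness, post-treatment | 1 |

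Sum: 1+1+2+1+1+4+1+4+1+4+1+1+1+2+1+1 = 27 entries. End-of-treatment ALT, AST and GGT in row 6 repeat rows 2 and 3, so 27 - 3 = 24 unique entries. Five of these are post-treatment versions of outcomes already listed, so the distinct outcomes number 24 - 5 = 19.

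**Step 3. Comparisons.** 27 x 3 = 81; 24 x 3 = 72. Rows 6 to 8 contain 4 + 1 + 4 = 9 variables with a time course. One extra time-course test for each gives 33 to 36 entries, or 99 to 108 comparisons, so 81 is not a ceiling.

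**Step 4. Consequence under each reading.**

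*Reading A: divisor held at 48, all 72 to 81 p-values ranked.* Before the step-up minimum, an adjusted p-value is p x m / rank. Using 48 for m scales it by 48/72 = 0.67 or 48/81 = 0.59. For independent tests the FDR equals q x m0/48, where m0 is the number of true null comparisons, and its maximum is q x m/48:

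- q = 5%: 0.05 x 72/48 = 7.5%; 0.05 x 81/48 = 8.4%.
- q = 10%: 15.0%; 16.9%.

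The first-rank threshold at q = 5% is 0.05/48 = 0.00104, against 0.05/72 = 0.00069 or 0.05/81 = 0.00062.

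Simulation gave the following FDR (40,000 runs, three doses sharing one placebo arm, variables otherwise independent, q = 5%, mean z of 3 for affected variables):

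| Variables truly affected | 72 tests, divisor 48 | 81 tests, divisor 48 | Divisor = number of tests (72 or 81) |
|---|---|---|---|
| None | 7.0% | 8.5% | 4.8% |
| A quarter | 5.6% | 6.2% | 3.7% to 3.8% |
| Half | 3.7% | 4.0% | 2.4% to 2.5% |

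This agrees with the formula within simulation error. By the formula, the FDR exceeds 5% only if more than 48 comparisons are true nulls.

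*Reading B: one variable per row adjusted.* The family is then 48, but 72 - 48 = 24 or 81 - 48 = 33 comparisons lie outside it. Which variable represents a row is not fixed in advance.

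*Reading C: Benjamini-Hochberg run on every p-value produced.* The divisor equals the number of tests, the FDR stays at or below q, and 48 is only a wrong count in the text.

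**Step 5. Direction of change.** Take four p-values of 0.004, 0.006, 0.010 and 0.012 with 44 larger ones. In the family of 48 all four have adjusted p = 0.012 x 48/4 = 0.144. Adding 33 null-like p-values gives 0.012 x 81/4 = 0.243. Adding 33 p-values of 0.001 instead gives 0.010 to 0.026. Enlarging the family can raise or lower an adjusted p-value.

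**The case against.** The best defence is that the multiplication is right and that Benjamini-Hochberg takes its divisor from the p-values it is given. Section 9.4.3 speaks of the presented p-values. If 72 or 81 are presented and all go into the procedure, control is kept. One joint test per row would also make 48 correct. The matter touches only secondary endpoints of a phase 2 trial, and estimates with 95% confidence limits are reported in any case.

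Much of this stands. A reader might infer that the plan necessarily under-corrects. The documents do not support that: it needs the divisor to stay at 48 while more p-values are ranked, and the text does not clearly prescribe this. Nor is 8.4% an expected error rate. It is a worst case, at an assumed level, with no real effects. A reader might also infer that a corrected count would make every adjusted p-value larger, but step 5 of the working shows otherwise.

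The defence does not remove the mismatch. The plan states 48 outright, describes no joint test, and offers no rule for choosing a variable. Under the most favourable implementation the figure is still wrong.

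**Conclusion.** The concern holds as a misspecified family. The 48 in Section 9.4.3 counts rows, while the list behind it contains 24 to 27 variable-by-period endpoints (19 distinct outcomes), hence 72 to 81 dose comparisons at one test per entry. The stated models cannot produce 48 p-values from this list.

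The effect on error control is conditional: a bound of 7.5% to 8.4% instead of 5% under Reading A, 24 to 33 unadjusted comparisons under Reading B, and no loss of control under Reading C. The percentages assume q = 5% and independent tests, and shrink as more effects are real. The counts rest only on the endpoint list. The primary Williams' test and the sample size are not affected.

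**What to change.** In Section 9.4.3, list every variable, period and time point that will receive a p-value, each once. Say whether time course gets its own test. Replace 48 with three times the number of entries (72 at one test per unique entry), run Benjamini-Hochberg over all of them, and state the FDR level.

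Alternatively, keep 48 by naming in advance one variable or one joint test for each row and reporting the remaining variables without p-values.

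Either is a text edit, best made before treatment codes are broken. It needs no new data or participants. The price is that some adjusted p-values may become larger, while others may become smaller.
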